4.6 Adjusting for baseline measure in change from baseline outcomes

Primary Objective 2 is change from baseline in length-for-age Z-score. Change from baseline outcomes will be adjusted for the baseline value in order to avoid the phenomenon of regression to the mean. In an analysis of covariance (ANCOVA) framework, this can be achieved by including baseline metric in the model. Identically, the same adjustment is achieved by including participant level covariates as random effects in a mixed effects model. This accounts for the clustering of length-for-age and weight-for-length across the two timepoints (enrolment and day 90) within each enrolled participant.

5 Hypotheses to be tested

Primary Objective 1 – 180 day mortality:

Null hypothesis: Among children 2-23 months of age with moderate to severe diarrhea, 180 day mortality is independent of treatment allocation to placebo or to a 3-day course of oral azithromycin.

Alternative hypothesis: Among children 2-23 months of age with moderate to severe diarrhea, 180 day mortality is not independent of exposure i.e. those allocated to receive a 3-day course of oral azithromycin compared to those allocated to receive oral placebo..

Primary Objective 2 – Change in Length-for-age z-score:

Null hypothesis: Among children 2-23 months of age with moderate to severe diarrhea, the mean change from baseline in length-for-age z-score (ΔLAZ) over the 90 day follow-up period is independent of treatment allocation to placebo or to a 3-day course of oral azithromycin.

Alternative hypothesis: Among children 2-23 months of age with moderate to severe diarrhea, the mean change from baseline in ΔLAZ over the 90 day follow-up period is not independent of exposure i.e. among those treated with a 3-day course of oral azithromycin than those treated with a placebo preparation.

Secondary objective 1 – Hospitalization by day 90

Null hypothesis: Among children 2 to 23 months of age with moderate to severe diarrhea, the proportion of children hospitalized by day 90 after enrolment, is independent of treatment allocation to placebo or to a 3-day course of oral azithromycin.

Alternative hypothesis: Among children 2 to 23 months of age with moderate to severe diarrhea, the proportion of children hospitalized by day 90 after enrolment, is not equal in the placebo arm and the arm receiving 3-day course of oral azithromycin.

Secondary objective 2 – Hospitalization or death by day 90

Null hypothesis: Among children 2 to 23 months of age with moderate to severe diarrhea, the proportion of children hospitalized or dying by D90 after enrolment, is independent of treatment allocation to placebo or to a 3-day course of oral azithromycin.

Alternative hypothesis: Among children 2 to 23 months of age with moderate to severe diarrhea, the proportion of children hospitalized or dying by D90 after enrolment, is not equal in the placebo arm and the arm receiving 3-day course of oral azithromycin.

Secondary objective 3 – Hospitalization or death by day 10

Null hypothesis: Among children 2 to 23 months of age with moderate to severe diarrhea, the proportion of children hospitalized or dying by day 10 after enrolment, is independent of treatment allocation to placebo or to a 3-day course of oral azithromycin.

Alternative hypothesis: Among children 2 to 23 months of age with moderate to severe diarrhea, the proportion of children hospitalized or dying by day 10 after enrolment, is not equal in the placebo arm and the arm receiving 3-day course of oral azithromycin.

Secondary Objective 4, 5 & 6 - Acute wasting:

Null hypothesis: Among children 2-23 months of age with moderate to severe diarrhea, the mean change from baseline in weight-for-length z-score (ΔWLZ), weight-for-age z-score (ΔWAZ) and mid-upper arm circumference ($\Delta MUAC$) over the 90 day follow-up period is independent of treatment allocation to placebo or to a 3-day course of oral azithromycin.

Alternative hypothesis: Among children 2-23 months of age with moderate to severe diarrhea, the mean change from baseline in weight-for-length z-score (ΔWLZ), weight-for-age z-score (ΔWAZ) and mid-upper arm circumference ($\Delta MUAC$) over the 90 day follow-up period is not independent of treatment allocation to placebo or to a 3-day course of oral azithromycin.

Secondary objective 7: descriptive report of prevalence of azithromycin resistant *E.coli* from stools provided at baseline by a sub sample of children enrolled into the trial.

Secondary Objective 8- Antibiotic resistance:

Null hypothesis: Among the subset of children 2-23 months of age with moderate to severe diarrhea selected to be in the AMR sub-study, the prevalence of resistance to azithromycin in *E. coli* and *S. pneumoniae* is greater than or equal to 10% points higher in the group randomized to a 3-day course of oral azithromycin than those randomized to placebo.

Alternative hypothesis: Among the subset of children 2-23 months of age with moderate to severe diarrhea selected to be in the AMR sub-study, the prevalence of resistance to azithromycin in *E. coli* and *S. pneumoniae* in the group randomized to a 3-day course of oral azithromycin is less than 10% points higher than in the group randomized to placebo.

The same hypothesis are also applicable to contacts

6 Data management and analysis processes, and procedures on breaking the intervention code

- 6.1. The data set on the WHO server called the ‘WHO dataset’ will be the final data set from which all ABCD analyses will be done, consistent with analyses for a multicentric trial.
- 6.2. The WHO coordination team will coordinate the analyses. The intellectual input for the analyses will be provided by all site PIs within the statistical analysis plan – dummy tables drawn up (which will be populated by a study statistician) and initial models specified. The WHO will ensure there is a statistically competent data analyst to support the analyses. A preliminary cleaning of the data required to confirm the main analyses (death and linear growth outcomes) will be done by the analyst. At this point, all investigators will remain blinded to the intervention each participant has been receiving.
- 6.3. The analyst makes a preliminary dataset that contains clean data required for the confirmatory main analyses (as in V9 of the protocol and table 2 and row 1 of table 3). The dataset and summary statistics for each variable, including missingness tables, are distributed to the principal investigators on the trial. Once these individuals agree that the data are sufficiently comprehensive and clean, the study statistician will run an analysis by blinded trial allocation arm.
- 6.4. The analyst will complete and present the preliminary analyses for the two created groups. Based on these analyses, the study statistician + investigators will make suggestions for the amendment of the Statistical Analysis Plan (SAP) (e.g. on the treatment of missing values). The plan is to break the code after the AMR analysis is completed. However, this may change if the AMR analysis is delayed beyond March 2020.
- 6.5. Before the intervention code is fully broken, mistakes found in the data can be corrected in the database, as long as there is an audit trail that indicates the date of correction, the old and new value, justification for the correction and the identity of the person authorizing the change (this is not necessary for the correction of entry errors). Any changes in the dataset will be incorporated into the WHO dataset after the discussion with the site and approval of the site PI and the WHO coordinator. After the code is broken, the data on main outcomes will be “frozen” and data can no longer be corrected in the database. Instead, all corrections (also entry errors) will be reviewed and need to be approved by the responsible investigator and WHO coordinator and documented.
- 6.6. A data analysis workshop is planned tentatively in March 2020, but was canceled as a result of the COVID pandemic. Instead this will be done online in May-June. The idea is that the initial analysis as specified in the SAP has been completed and shared with all sites. Therefore, this workshop will facilitate further exploration of questions that arise

from the initial analyses, modification of models etc. and development of the manuscript. Ideally, the plan is to finalize the main trial paper and AMR analyses (resistance to azithromycin) at the same time, if this is possible.

- 6.7. Country level analyses: To ensure integrity of multiple reports/ publications from the ABCD trial, the same WHO dataset should be used for all analyses. No enrolments may be added to or deleted from this dataset. For country level analyses, where additional variables may be available, these should be appended onto the WHO dataset for the specific site and then analyzed.

7 Definition of the outcomes

7.1 180 day mortality (and 10 day and 90 day mortality outcomes)

Definition of 180 day Mortality: Death due to any cause occurring ≤ 180 days post-randomization. The day of enrolment in the trial is termed “Study Day 1” therefore 180 days post enrollment is Study Day 181. All deaths or censoring events occurring from enrolment and up to and including Study Day 181 will be included in the primary analysis of the mortality outcome. Deaths and censoring events occurring on or after Study Day 182 (181 days since enrolment) will not be included in the analysis. Other mortality outcomes such as death by day 10 (part of Secondary Outcome 4) and day 90 (part of Secondary Objective 6) will also be defined on basis that day of enrolment is termed “Study Day 1”, making these outcomes on Study Day 11 and 91 respectively.

Date of death:

The date of death may be extracted *in ordered preference* from:

1. Death certificate
2. Hospital or clinic record
3. Caregiver other official written record
4. Caregiver recall

Note that forms do not currently record source of death date. Local SOP's should outline the above ordered preference.

Date of death currently appears on three forms (“Form 08-Vital Status”; “Form 11-SAE”; and on the verbal autopsy form). In cases of conflict among forms, the date appearing on Form 08-Vital Status should be prioritized over other forms.

7.2 Length-for-age Z-score (LAZ):

Length for age will be determined from age, sex, and length information at the date of enrolment (day 1) and date of D 90visit (day 91 up to day 101) of participant age, using the macro developed by the WHO using the WHO 2006 multi-centre growth standard. The LAZ values will be rounded to two decimal points.

7.3 Weight-for-age Z-score (WAZ):

Weight for age will be determined from age, sex, and weight information at the date of enrolment (day 1) and date of final visit (day 91 up to day 101) of participant age, using the macro developed by the WHO using the WHO 2006 multi-centre growth standard. The WAZ values will be rounded to two decimal points.

7.3 Weight-for-length Z-score (WLZ):

Weight for length will be determined from age, sex, length and weight information at the date of enrolment (day 1) and date of final visit (day 91 up to day 101) of participant age, using the macro developed by the WHO using the WHO 2006 multi-centre growth standard. The WLZ values will be rounded to two decimal points.

7.4 Hospitalization:

First episode of overnight stay in a health facility per child occurring within 10 days from enrolment by trial records

First episode hospitalizations per child occurring within 90 days from enrolment by trial records or parent or caregiver report of overnight stay in a health facility

7.5 Azithromycin resistance

Clinical Minimum inhibitory concentrations (MIC) cut-offs corresponding to non-susceptibility from the 2020 Clinical and Laboratory Standards Institute (CLSI) will be used for defining azithromycin resistance. MICs exceeding the established cut-points corresponding to resistance and intermediate will be considered as “resistant” to maximize likelihood of detected potential signals of declining susceptibility.

7.6 Serious adverse event

At least one episode within 10 days from enrolment of any event defined as a serious adverse event in Standard Operating Procedure 10, of 14 February 2019. Other serious events (anaphylactic reaction, convulsions, severe colitis, other) will be described by trial arm.

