6.4 Outcome measurements

- **Mortality** and date of death to be ascertained at the DAY 45 contact, the DAY 90 and DAY 180 visits, or at any other time point during the 180-day study period. **Verbal and Social Autopsies (VASA)** will be attempted for all recorded deaths within the study period. As part of the VASA autopsy procedures for deaths that occur in facilities, we will collect all available relevant information (diagnostics, treatment and drugs, etc.) from the medical record file of the study subject.
- **Hospitalizations** (number and categorized causes) between days 0 and 180
- **Anthropometric measurements:** length or height, weight and MUAC will be measured at enrolment and at the DAY 90 visit.
- **Antimicrobial resistance** prevalence of phenotypic resistance to selected antibiotics in isolated *E. coli* (stool sample), and *S. pneumoniae* (naso-pharyngeal swabs) at enrolment, at DAY 90 and at DAY 180 will be measured on a sub-sample. Additionally, stool samples will be stored from all children at enrolment, to facilitate later molecular identification of diarrhea etiologies, gut microbiota, and antimicrobial resistance genes in stool bacteria. For the same purpose, stool and nasopharyngeal swab samples will be stored on DAY 90 and DAY 180 from the sub-sample of children (see sections 6.5 and 6.6 for further details).

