7. SERIOUS ADVERSE EVENTS

Serious Adverse Events (SAE) will be recorded from enrolment to DAY 10 (7 days after the end of study intervention). Data on mortality and hospitalizations will be collected until DAY 180.

At enrolment, caregivers will be told to come back to the health facility if the enrolled child present any of the following signs in the following 10 days:

- Anaphylactic reaction, Quincke oedema, convulsions, cutaneous rash, arthralgia, urticaria, and severe colitis.

On DAY 2 and DAY 3 visit for the DOT, the study worker will record any reported SAE.

In case there is a suspected allergic reaction caused by the study drug or other SAE, the participant will not get any further doses of the study drug. In case of a suspected allergic reaction, the study data manager at WHO will break the randomization code for that participant, to know which product the participant was receiving. The data manager will provide this

information to clinicians taking care of the participant, so that they can take into account in the medical management and also counsel the participant's caregivers about any need to avoid certain drugs in future.

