11. RISK MITIGATION

Azithromycin is approved for infants older than 6 months of age and has been widely used without significant safety concerns in neonates and infants for a wide-range of bacterial infections. Safety and pharmacokinetics have been evaluated in newborn infants with gestational ages as low as 24 weeks (13). While several case reports of pyloric stenosis have

been reported in infants receiving azithromycin, the FDA OND Maternal Health Team concluded in 2010 that available data do not demonstrate an association between azithromycin use and increased risk of pyloric stenosis². However, to monitor possible incidence of this adverse reaction, all study participants will be queried about hospitalizations (for abdominal surgery, for diarrhoea and for some other defined causes) at the day 45 and day 90 follow-up visits.

Large-scale use of antibiotics raises concern for the possibility that antimicrobial resistance will be induced and ultimately could negatively impact clinical outcomes in the communities in which resistance emerges. Several studies have examined the emergence of antibiotic-resistance among pharyngeal pneumococcal isolates following mass treatment with azithromycin (9). Multiple studies have documented relatively rapid emergence of macrolide resistance following mass drug administration with azithromycin (9) although rates of resistance decline quickly after discontinuation of treatment (12). To monitor possible incidence, spread, and disappearance of antimicrobial resistance, a subgroup of participants and their siblings or close household contacts will be asked to provide stool and naso-pharyngeal swab specimens before, during, and after the trial intervention, as described in more detail in section 6.5.

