9.3 Analysis of secondary objectives 1, 2 and 3 - Hospitalization

Following an episode of high risk diarrhea without dysentery among children 2 to 23 months of age living in low resource settings who are randomized to receive a 3-day course of azithromycin or placebo, comparison by trial allocation arm of:

1. proportion of children hospitalized or died in the initial 10 days following enrolment.
2. proportion of children hospitalized in the 90 days following enrolment.
3. proportion of children hospitalized or died in the 90 days following enrolment.

Primary event considered will be the first episode of hospitalization per child. Hospitalization rates will be reported by country to understand heterogeneity across sites. Risk ratio will be estimated from a model including trial allocation and country of enrollment. Adjusted analysis will include effect modifying covariates, and sensitivity analysis will include unbalanced potential confounders by trial arm.

Hospitalization data are available as binary outcomes only, and date of hospitalization is missing for all events after 10 days of follow-up. Time to event analysis is not possible for the hospitalization outcome.

Since likelihood of hospitalization may cluster by clinic, the following log-binomial mixed effects model is proposed:

$$\log \Pr(Y_i = 1) = \beta_{0c} + \beta_1 C_i + \beta_2 Z_i \times 1_{\{t>t_0\}} + \varepsilon_i \quad - \text{Model 6}$$

Where

$$Y_i = \begin{cases} 1 & \text{hospitalized at least once by day 180} \\ 0 & \text{not hospitalized} \end{cases}$$

Under this definition we are accounting for clustering at clinic level. The b term is a random effects for the c^{th} clinic, and take account of the variance due to clustering within clinic.

The term $\beta_1 C_i$ is the fixed effect of country, with C_i representing the country of enrolment for child i .

The term $\beta_2 Z_i$ is the fixed effect of azithromycin, with Z_i representing the treatment allocation for child i where

$$Z_i = \begin{cases} 1 & \text{azithromycin} \\ 0 & \text{placebo} \end{cases}$$

The term ε_{ij} is the variance component due to random error for child i at time j .

Adjusted analysis will include individual level effect modifiers, thus:

$$\log \Pr(Y_i = 1) = \beta_{0c} + \beta_1 C_i + \beta_2 Z_i \times 1_{\{t>t_0\}} + \beta_{3X} \mathbf{X}_{ij} + \varepsilon_i \quad - \text{Model 7}$$

Where \mathbf{X}_{ij} is the vector of effect-modifying covariates of child i at time j :

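### The SAP plans no analysis of hospitalization by cause, so the protocol's pyloric stenosis monitoring at days 45 and 90 has no clear by-arm display after day 10

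*SAP*

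**What the plan says.** **Protocol.** Section 11 mentions case reports of pyloric stenosis in infants given azithromycin. It reports a regulatory conclusion that "available data do not demonstrate an association between azithromycin use and increased risk of pyloric stenosis", and still commits to monitoring: "all study participants will be queried about hospitalizations (for abdominal surgery, for diarrhoea and for some other defined causes) at the day 45" contact, and again at day 90. Section 6.4 lists hospitalizations among the outcome measurements as "number and categorized causes) between days 0 and 180". Sections 6.1 to 6.3 collect admissions at the day 45, 90 and 180 contacts. Section 7 sets a shorter window for serious adverse events: "Serious Adverse Events (SAE) will be recorded from enrolment to DAY 10".

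**SAP.** Section 7.6 defines the serious-event outcome as "At least one episode within 10 days from enrolment of any event defined as a serious adverse event in Standard Operating Procedure 10", and adds: "Other serious events (anaphylactic reaction, convulsions, severe colitis, other) will be described by trial arm". Section 3.3, item 3, calls for the 10-day proportion by arm. Section 7.4 defines hospitalization as the first overnight stay per child, with no cause. Section 9.3 models it as a yes/no outcome and states: "Hospitalization data are available as binary outcomes only". It also says that admission dates are missing after day 10. Table 4 has all-cause hospitalization and hospitalization-or-death rows only. Neither of the two tables numbered 6 has a row for serious events or for cause of admission.

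**The concern.** The protocol uses two safety instruments with different reach: serious-event recording to day 10, and cause of admission after that. The SAP carries the first forward and drops the second. Under the SAP as written, an abdominal-surgery admission on day 20, reported at the day 45 contact, adds one to an all-cause count. If the child had already been admitted for something else, it adds nothing, because only the first episode counts.

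At stake is whether the trial report can say anything by arm about a reaction that the protocol chose to monitor. The youngest children make this relevant: enrolment starts at 2 months, while section 11 describes approval for infants older than 6 months. There is also a plain conflict about the data. Protocol 6.4 promises counts and causes; SAP 9.3 says that only a binary variable exists. If 9.3 is literally right, a listed outcome was not captured, and the plan does not say so.

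**Working it through.** The plan states no figure on this point, so the main check is a comparison of text.

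| Item | Protocol | SAP |
|---|---|---|
| Serious adverse events | enrolment to day 10 (7) | 10 days (3.3, 7.6): agrees |
| Cause of admission, days 45 and 90 | asked of all participants (11) | no analysis, no table row |
| Count and causes to day 180 | listed outcome (6.4) | first any-cause episode, yes/no (7.4, 9.3) |
| Serious-event proportion by arm | – | required by 3.3, item 3; no row in the tables |

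**Window.** The serious-event analysis covers 10 of the 90 days over which section 11 asks about admissions. The remaining 80/90 = 89% has no planned display by cause.

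**Illustration of what pooling all causes hides.** The documents give no admission rates, so these are assumptions: all-cause admission by day 90 of 2%, 5% or 10%, and n = 5,750 per arm (planned size, protocol 10.3).

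SD of the between-arm difference in counts = √(2·n·p·(1−p)):
- p = 2%: √(2 × 5,750 × 0.02 × 0.98) = 15.0; six extra admissions = 6/15.0 = 0.40 SD
- p = 5%: √(2 × 5,750 × 0.05 × 0.95) = 23.4; 6/23.4 = 0.26 SD
- p = 10%: √(2 × 5,750 × 0.10 × 0.90) = 32.2; 6/32.2 = 0.19 SD

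Tabulated by cause, 6 versus 0 gives an exact two-sided p = 2 × 0.5⁶ = 0.031. This is the smallest split against zero that falls below 0.05 (5 versus 0 gives 2 × 0.5⁵ = 0.0625). It shows the contrast and is not a forecast.

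**Power, same purpose.** Assume 0.02% abdominal-surgery admissions on placebo and three possible excesses on azithromycin (two-sided Fisher test at 0.05 for the by-cause columns):

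| Excess | By cause, 5,750 per arm | By cause, 5,175 per arm (10% lost) | All-cause, 5,750 per arm, placebo 2–10% |
|---|---|---|---|
| 0.1% | 40% | 33% | 6–4% |
| 0.2% | 89% | 84% | 11–5% |
| 0.3% | 99% | 98% | 20–8% |

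**If no case occurs in an arm.** The rule-of-three upper 95% bound is 3/n:
- all children: 3/5,750 = 0.052%
- infants, using the protocol 10.3 assumption that half are under 12 months: 3/2,875 = 0.10%

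SAP section 2 reports that recruitment was halted, with the last participants enrolled on July 10, 2019, and gives no final number. At an assumed 4,000 per arm the all-children bound would be 3/4,000 = 0.075%. It would be wider again for children under 6 months and after loss to follow-up.

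**The case against.** The strongest defence has four parts.

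- **The protocol promises a question, not an analysis.** Protocol 10.2 itself plans only all-cause hospitalization proportions, so the SAP follows it. This is true, and the gap begins there. But section 10 introduces itself as an outline for the primary objectives, section 6.4 lists causes as an outcome, and the SAP's version history gives alignment with the protocol as a purpose of version 1.0.
- **Safety oversight exists elsewhere.** The data safety and monitoring board receives serious-event summaries (12.5), and monthly progress reports count hospitalizations (12.6). Neither is described as showing cause of admission by arm, and serious events stop at day 10.
- **The prior concern is weak.** Section 11 says that no association has been shown. The protocol nevertheless chose to monitor, and a descriptive table is proportionate to that.
- **The data may not exist.** SAP 9.3 may mean that causes and repeat admissions cannot be recovered. That stands as a practical limit, and the fix has to allow for it.

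Some stronger readings are tempting but unsupported. A reader might infer that the 10-day window in SAP 7.6 is an error; it matches protocol 7. A reader might infer that a case could never be seen by arm; one in the first 10 days could appear in the open category of other serious events in 7.6, and causes, if recorded, could be tabulated afterwards. A reader might also infer that pyloric stenosis is the only drug-related question in section 11. Antimicrobial resistance is the other, and SAP 9.5 and 9.6 analyse it at length.

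**Conclusion.** The point holds in a limited form. The SAP drops a protocol-listed outcome, cause of hospitalization, and with it the only instrument that the protocol sets for pyloric stenosis after day 10. No planned analysis clearly shows abdominal-surgery admissions by arm from then on, and SAP 9.3 contradicts protocol 6.4 on what was collected. The missing serious-event row is a smaller omission, since 3.3 and 7.6 already commit to reporting that proportion.

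This does not touch the primary outcomes and is not evidence of harm. The textual finding needs no assumption. The sizes do: they rest on assumed admission rates and on the planned 5,750 per arm, which is likely more than were enrolled given the early halt. Across the assumed range the contrast is stable: a handful of surgical admissions is lost in the all-cause count (0.19–0.40 SD) but visible when tabulated by cause. It is worth correcting as a cheap improvement to safety reporting.

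**What to change.** **If causes were captured**, add to SAP 3.3, 7.4 and the tables a descriptive count by arm of children with any admission (not only the first) for abdominal surgery, and for each other recorded cause, by day 90 and by day 180. Show it overall and for children under 6 months, an age band that SAP 4.5 already uses. Give exact confidence intervals, with denominators being the children actually enrolled and followed. No hypothesis test is needed. Add the day-10 serious-event row by arm that 3.3, item 3, requires.

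**If causes or repeat admissions were not captured**, reconcile SAP 9.3 with protocol 6.4 and 11, and state in the SAP and the report that the planned monitoring could not be delivered.

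**Cost.** One extra table and one extra row, with no new visits or tests, provided that the causes are in the database; 9.3 leaves that open. The downside is few events and low precision, so the table should be labelled descriptive.
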